2.2. Study Objectives and Endpoints

Objectives	Endpoints
Primary	Primary

 To compare the effect of UMEC/VI (62.5/25 mcg once daily) with UMEC (62.5 mcg once daily) on lung function 	
 Change from baseline in trough Forced Expiratory Volume in One Second (FEV₁) at week 24
Secondary	Secondary

 To compare UMEC/VI (62.5/25 mcg once daily), UMEC (62.5 mcg once daily) with salmeterol (50 mcg twice daily) on patient reported outcomes (PROs) 	
 Change from baseline in self administered computerised (SAC) transient dyspnea index (TDI) Percentage of TDI responders according to SAC TDI score. A responder is defined as a ≥ 1 unit improvement in SAC TDI score Assessment of respiratory daily symptoms over 24 weeks using Evaluating Respiratory Symptoms- COPD (E-RS) and its subscales (breathlessness, cough and sputum and chest symptoms) Percentage of E-RS responders according to E-RS score (defined as reduction in E-RS score of ≥ 2 or ≥ 3.35 units) from baseline Change from baseline in St George's Respiratory Questionnaire (SGRQ-C) Percentage of responders according to SGRQ-C total score (defined as a 4 point or greater reduction from baseline) Change from baseline in COPD assessment test (CAT) Percentage of responders according to CAT

Objectives	Endpoints
	(defined as a ≥ 2 unit improvement in score from baseline)

 To compare UMEC/VI (62.5/25 mcg once daily), UMEC (62.5 mcg once daily) with salmeterol (50 mcg twice daily) on other COPD efficacy measures 	
 Ratio to baseline of trough Forced Expiratory Volume in One Second (FEV₁) Time to first mild, moderate or severe exacerbation Time to first moderate or severe exacerbation Time to first severe exacerbations Time to first clinically important deterioration (CID) composite endpoint Time to first clinically important deterioration composite endpoint excluding FEV₁ (Exacerbation, SGRQ, TDI, CAT) Rescue albuterol/salbutamol use, (percentage of rescue-free days and mean number of Inhalations/day) captured by the electronic diary (eDiary) over 24 weeks Inspiratory capacity (IC) Forced Vital capacity (FVC) Change from baseline in trough FEV₁ Change from baseline in global impression of disease severity

Objectives	Endpoints
Safety	Safety

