5.2. Baseline Definitions

For all endpoints (except as noted in baseline definitions) the baseline value will be the latest pre-dose assessment with a non-missing value, including those from unscheduled visits. If time is not collected, Day 1 assessments are assumed to be taken prior to first dose and used as baseline.

Endpoint	Baseline derivation
Trough FEV ₁ , FVC and IC	The mean of the values measured at 30 min and 5 min pre-dose on Day 1. If the actual time of an assessment is after the time of dosing on Day 1, the value at that assessment will be

Endpoint	Baseline derivation
	
set to missing prior to calculating baseline.
 
If one of the values is missing then the baseline will be the single remaining value; otherwise the baseline will be the mean of the two values.

TDI	
BDI assessment taken prior to dosing on Day 1.
 
The baseline dyspnea index (BDI) focal score will be calculated as the sum of the ratings recorded for each of the three individual scales (Functional Impairment, Magnitude of Task, Magnitude of Effort). Each of these scales has five possible scores ranging from 0 to 4 (with lower scores indicating more impairment), so the range of the BDI focal score is 0 to 12. If a score is missing (or has a value of W, X or Y) for any of the three scales, then the BDI focal score will be set to missing.

E-RS and subscale scores	Average of measurements from day -28 to day -1 inclusive; at least 16 days must be non-missing.
Physical activity	Average of measurements prior to randomisation; at least 3 days must be non-missing.
Rescue Use - Mean Number of Puffs of Rescue Medication Per Day and Percentage of Rescue-free Days Over Weeks 1-24 captured using e-diary	
The total puffs of rescue for each day will be calculated as number of salbutamol puffs. If the number of puffs is missing then the total puffs will be set to missing for that day.
 
The baseline number of inhalations is calculated using the mean number of total inhalations and the baseline percentage rescue use is calculated from the percentage of rescue free days as the average of measurements from day -28 to day -1 inclusive; at least 14 days must be non-missing.

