7.2. Secondary Efficacy Analyses

7.2.1. Endpoint / Variables

- 1) SAC TDI focal score
- 2) Assessment of respiratory daily symptoms using E-RS and its subscales
- 3) Change from baseline in SGRQ
- 4) Change from baseline in CAT
- 5) Proportion of responders according to SAC TDI focal score
- 6) Proportion of responders according to E-RS total and subscale scores
- 7) Proportion of responders according to SGRQ total score
- 8) Proportion of responders according to CAT score
- 9) Time to first on-treatment mild/moderate/severe COPD exacerbation
- 10) Time to first on-treatment moderate/severe COPD exacerbation
- 11) Time to first on-treatment severe COPD exacerbation
- 12) Time to CID composite endpoint (including individual components)
- 13) Time to CID composite endpoint excluding FEV1 (including individual components)
- 14) Mean number of inhalations of rescue use per day (using eDiary)
- 15) Percentage of rescue-free days (using eDiary)
- 16) Trough FEV1 ratio to baseline
- 17) Trough FVC
- 18) Trough IC
- 19) Subject global rating of change in COPD severity

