
standard errors (SEs) will be presented for each treatment by visit, together with estimated treatment differences (UMEC/VI 62.5/25 vs. UMEC 62.5, UMEC/VI 62.5/25 vs Salmeterol and UMEC 62.5 vs Salmeterol), corresponding 95% CIs and p-values.
 
 • A plot of LS mean changes from baseline and 95% CIs for each treatment by visit will be generated. • A plot of LS mean treatment differences and 95% CIs between the treatment groups by visit will also be generated.
Summary Results Presentation

 • Summary of baseline FVC will be presented by treatment for all subjects. • Summary statistics for raw and change from baseline in trough FVC at each visit and for each treatment will be presented on the same table. • Summary of baseline IC will be presented by treatment for all subjects. • Summary statistics for raw and change from baseline in trough IC at each visit and for each treatment will be presented on the same table.

Subject Global Ratings of Change

Secondary Statistical Analysis
Endpoints

 • Subject global rating of COPD severity • Subject global rating of change in COPD Severity
Model Specification

 • Change of Severity will be analyzed using a generalized linear mixed model with treatment as an explanatory variable and visit, stratum (no. of bronchodilators per day during run-in), geographical region, visit by treatment interactions included as covariates.
Model Checking

 • Pearson residuals will be plotted by using PLOTS=RESIDUALPANEL option for the model statement in SAS..
Model Results Presentation

 • Number and percentage of subjects reporting each category of change at each visit • P-value for comparison between UMEC/VI 62.5/25 vs. UMEC 62.5, UMEC/VI 62.5/25 vs Salmeterol and UMEC 62.5 vs Salmeterol for change. • UMEC will be used as the reference level for treatment for the comparison between UMEC/VI vs. UMEC. Salmeterol will be used as the reference level for treatment for the comparison between UMEC/VI vs. Salmeterol and UMEC vs Salmeterol.

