10. APPENDICES

10.1. Appendix 1: Schedule of Activities

10.1.1. Protocol Defined Schedule of Events

			Blinded Treatment					
Visit	Pre-screen ¹ 0	Screen/ Run-in 1	Rando- mization 2	3	4	5	EW Visit ²	Telephone Follow up contact 6
Week	-10 to -4	-4	0	4	12	24		
Day	-70 to -28	-28	1	28	84	168		7 days after V5 or EW Visit
Window	-7/+2 days	-7/+2 days	-7/+2 days	-7/+2 days	-7/+2 days	-7/+2 days		±3 days
Screen/Baseline								
Informed consent	X							
Demography	X							
Medical/COPD history		X						
Smoking history/status		X						
Smoking cessation counselling		X						
Concomitant medication assessment	X	X	X	X	X	X	X	X
Height and weight		X						
Cardiovascular History/family history of premature CV disease)		X						
Screening spirometry (including post bronchodilator testing) ³		X						
CAT questionnaire		X	X					
Verify Inclusion/Exclusion Criteria		X						
Training on use of inhalers		X	X					
Training on use of eDiary and eMDI		X	X					
Verify randomization Criteria			X					

			Blinded Treatment					
Visit	Pre-screen ¹ 0	Screen/ Run-in 1	Rando- mization 2	3	4	5	EW Visit ²	Telephone Follow up contact 6
Week	-10 to -4	-4	0	4	12	24		
Day	-70 to -28	-28	1	28	84	168		7 days after V5 or EW Visit
Window	-7/+2 days	-7/+2 days	-7/+2 days	-7/+2 days	-7/+2 days	-7/+2 days		±3 days
Register Visit in InForm	X	X	X	X	X	X	X	X
Register Visit in RAMOS NG	X	X	X	X	X	X	X	X
Efficacy/HRQoL assessments								
Spirometry, including pre-dose FEV ₁ , trough FEV ₁ and inspiratory capacity			X	X	X	X		
SAC BDI questionnaire ⁴			X					
SAC TDI questionnaire ⁴				X	X	X		
SGRQ-C questionnaire ⁴			X	X	X	X		
CAT questionnaire ⁴		X	X	X	X	X		
EXACT/ER-S: COPD ⁵		—————→						
Patient Global Rating of COPD severity			X	X	X	X		
Patient Global Rating of Change in COPD				X	X	X		
Safety assessments								
Adverse events/Serious adverse events ⁶	X	X	X	X	X	X	X	X
COPD exacerbation assessment	X	X	X	X	X	X	X	X
12-Lead ECG		X						
Urine pregnancy test ⁷		X	X			X	X	
Pharmacogenetic sample ⁸			←———— X —————→					
Medication/Supplies								
Dispense rescue albuterol/slabutamol. Dispense MDI ⁹		X	X	X	X	X		
Assess COPD medication compliance ¹⁰ during run-in			X					
Dispense eDiary		X						
Assess compliance with eDiary during run-in			X					
Collect rescue albuterol/slabutamol.			X	X	X	X	X	

			Blinded Treatment					
Visit	Pre-screen ¹ 0	Screen/ Run-in 1	Rando- mization 2	3	4	5	EW Visit ²	Telephone Follow up contact 6
Week	-10 to -4	-4	0	4	12	24		

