2.63	ITT	Analysis of Percentage of Rescue-Free Days over Weeks 1-24 using e-Diary		SAC
2.64	ITT	Summary of Mean Number of Occurrences of Rescue Medication per Day using eMDI.		SAC
2.65	ITT	Analysis of Mean Number of Occurrences of Rescue Medication per Day over Weeks 1-24 using eMDI		SAC
2.66	ITT	Summary of Percentage of Rescue-Free Days using eMDI		SAC
2.67	ITT	Analysis of Percentage of Rescue-Free Days over Weeks 1-24 using eMDI		SAC
Subject Global Ratings				
2.68	ITT	Summary of Subject Global Rating of COPD Severity		SAC
2.69	ITT	Summary and Analysis of Subject Global Rating of Change in COPD Severity	Use gsk2834425/ctt116853 as reference	SAC
Physical Activity Monitor				
2.70	AM	Summary of Weekly Mean Step Count		SAC

Efficacy: Tables				
No.	Population	Title	Programming Note	Deliverable
2.71	AM	Analysis of Weekly Mean Step Count		SAC
2.72	AM	Summary of Weekly Mean Duration of Light Physical Activity (Hours)		SAC
2.73	AM	Analysis of Weekly Mean Duration of Light Physical Activity (Hours)		SAC
2.74	AM	Summary of Weekly Mean Duration of Moderate to Vigorous Physical Activity (Hours)		SAC
2.75	AM	Analysis of Weekly Mean Duration of Moderate to Vigorous Physical Activity (Hours)		SAC
2.76	AM	Summary of Weekly Mean Total Energy Expenditure (kCal)		SAC
2.77	AM	Analysis of Weekly Mean Total Energy Expenditure (kCal)		SAC

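### The declared secondary endpoint on global disease severity has no planned treatment comparison; only the separate rating of change is modelled

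*SAP*

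**What the plan says.** Section 2.2 of the SAP places "Change from baseline in global impression of disease severity" among the secondary endpoints, under an objective to compare the three treatments on other efficacy measures.

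The schedule in Section 10.1.1 has two separate rows. "Patient Global Rating of COPD severity" is marked at Visits 2, 3, 4 and 5. "Patient Global Rating of Change in COPD" is marked at Visits 3, 4 and 5 only. Section 5.2 gives a default baseline rule that would serve the severity rating: "the baseline value will be the latest pre-dose assessment with a non-missing value".

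The secondary list in Section 7.2.1 contains one global item, number 19: "Subject global rating of change in COPD severity". Section 7.2.2 assigns it an odds ratio. The methods box in Section 7.2.5.1 names two endpoints, the first being "Subject global rating of COPD severity" and the second the rating of change, but it specifies one model: "Change of Severity will be analyzed using a generalized linear mixed model with treatment as an explanatory variable and visit, stratum", followed by region and the visit-by-treatment term.

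In Section 10.8.4, Table 2.68 is titled "Summary of Subject Global Rating of COPD Severity", without analysis. Table 2.69, for the rating of change, carries both summary and analysis. The maintenance-naive displays repeat this split in Tables 2.124 and 2.125.

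**The concern.** An endpoint that Section 2.2 declares as a comparison between arms should be traceable to a derivation, a model and a display. This one is not. The operative sections follow a different item, one that has no baseline value because it is not collected before treatment.

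Section 2.4 lets every secondary comparison be declared significant at 0.05 once the primary comparison succeeds. For this endpoint the plan does not fix which test that would be. After unblinding, an analyst could claim that either rating answers Section 2.2, and could choose how change in the severity rating is derived and modelled. The plan should close that choice in advance.

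A smaller point sits beside it. The repeated-measures models for the other patient-reported outcomes include a baseline score and its interaction with visit, with BDI taking that role for TDI. The rating-of-change model has no such term, although a severity rating is taken at Visit 2.

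**Working it through.** The plan states no figure for this endpoint, so the check is a trace of each rating through the SAP.

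| Step | Severity rating | Rating of change |
|---|---|---|
| Declared endpoint (2.2) | Yes, as change from baseline | Not named |
| Collected (10.1.1) | Visits 2, 3, 4, 5 | Visits 3, 4, 5 |
| Baseline available (5.2) | Yes, Visit 2 by the default rule | None |
| Secondary list (7.2.1) | Absent | Item 19 |
| Summary measure (7.2.2) | None | Odds ratio |
| Named in the methods box (7.2.5.1) | Yes | Yes |
| Model (7.2.5.1) | None | One, with no baseline term |
| Displays, all subjects | Table 2.68, summary only | Table 2.69, summary and analysis |
| Displays, maintenance-naive | Table 2.124, summary only | Table 2.125, summary and analysis |
| Replacement recorded (Table 1, Section 2.1) | No | No |

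Only the severity rating can yield a change from baseline, since it alone has a pre-treatment value. Its column has no entry for the secondary list, the summary measure or the model, and none of its displays is described as showing change from baseline or a treatment contrast.

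Table 1 records that the protocol's other endpoints were promoted to secondary. It does not record that one global rating replaced the other.

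The model sentence speaks of change of severity, which on its own could mean change in the severity rating. Three things point the other way. The results to be shown are the categories of change at each visit, item 19 names the rating of change, and only Table 2.69 is marked for analysis. If the sentence did mean the severity rating, the plan would still lack a derivation of change and a baseline term, and Table 2.68 would contradict it.

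Count of what is missing:

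- Treatment comparisons (7.2.5.1): 3.
- Post-baseline visits with a severity rating (Weeks 4, 12 and 24): 3.
- Contrasts without a planned estimate: 3 × 3 = 9. Section 2.2 gives no time point for this endpoint; if only Week 24 were intended, the count is 3 × 1 = 3.

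**The case against.** The strongest reply is that Section 2 only summarises the protocol, while Sections 7.2.1, 7.2.2, 7.2.5.1 and the display list agree with one another on a single analysed endpoint. Section 2.2 speaks of a global impression, which is the exact name of neither item in the schedule. A rating of change made after randomisation is itself a measure of change, so Section 2.2 may be loose wording for item 19. On that view the severity rating is meant to be described and the rating of change tested.

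This stands in part. The sponsor may well have intended it, and a renamed endpoint would then be enough. But the wording in Section 2.2 fits the item that has a baseline, the methods box lists both items as endpoints, and Table 1 is silent. The document does not settle the matter.

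Three stronger readings are tempting and should not be drawn:

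- A reader might infer that the severity rating is ignored altogether. It is summarised by arm in Tables 2.68 and 2.124. What is missing is a treatment comparison.
- A reader might infer that the rating of change is distorted by recall or by the patient's present state. The SAP does not show the wording of the item, so nothing in it supports that. Nor does leaving out a baseline covariate bias a randomised comparison.
- A reader might put a figure on the precision lost by omitting Visit 2 severity. The SAP gives no correlation between the ratings. A squared correlation on a linear scale would not transfer to a model that reports odds ratios.

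It is also fair to say that testing both ratings has a cost. Under Section 2.4 each comparison is tested at an unadjusted 0.05, so nine contrasts would become 9 + 9 = 18.

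**Conclusion.** The point holds as a gap between a declared secondary endpoint and its analysis. Followed as written, the SAP gives no treatment comparison for change from baseline in global severity, although Section 2.4 admits inference on it. The size is one secondary endpoint and up to nine contrasts, on the assumption that all three post-baseline visits count. The primary comparison and the other secondary endpoints are untouched. The absent baseline term in the rating-of-change model is a lesser matter: it is a chance to use a value already collected, not a source of bias.

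The conclusion rests on reading the two schedule rows as separate items, which their different visits support, and on the visible text of Table 1. It is worth correcting before unblinding, because the ambiguity is about which test supports a claim.

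**What to change.** In Section 7.2.5.1, add an ordinal repeated-measures model for the severity rating at Weeks 4, 12 and 24. Its terms should be treatment, visit, stratum, region, Visit 2 severity, visit by baseline and visit by treatment, and it should report odds ratios with confidence intervals for the three comparisons. This assumes that the rating is an ordered category scale, which the SAP does not show. Retitle Tables 2.68 and 2.124 as summary and analysis.

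Add Visit 2 severity as a covariate to the rating-of-change model. In the same edit, state that model's distribution and link, and list the odds ratio among its results: Section 7.2.2 promises one, whereas the methods box presents only p-values.

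State in Sections 2.2 and 7.2.1 that the severity rating carries the inference under Section 2.4 and that the rating of change is supportive. The number of comparisons tested at 0.05 then does not grow. If the sponsor instead intends the rating of change as the endpoint, rename it in Section 2.2 and record this in Table 1.

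The cost is SAP wording, one extra model, one covariate and two revised tables, all on data already scheduled. The downside is extra unadjusted comparisons if neither rating is made supportive.

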2.3. Study Design

Overview of Key Study Design Features	
Design Features:	
 • Multi-centre, randomized, double blind, double dummy, 3-arm parallel group study to compare Umeclidinium/Vilanterol, Umeclidinium, and Salmeterol in subjects with chronic obstructive pulmonary disease (COPD). • Approximately 3232 subjects will be screened, such that 2424 subjects will be randomized and approximately 2181 evaluable subjects complete the study. • Eligible subjects will be stratified by country, long-acting bronchodilator usage during the run-in (none or one long-acting bronchodilator per day) and activity subset (activity subset or no activity subset), and randomized in a ratio of 1:1:1 to UMEC/VI inhalation powder (62.5/25 mcg once daily) administered via the ELLIPTA inhaler, or UMEC (62.5 mcg once daily) administered via the ELLIPTA or salmeterol (50 mcg BID) administered via the DISKUS. Note the activity subset was only included as a randomisation stratification group for logistical purposes. • A subset of subjects up to 150 per treatment arm will undergo assessment of their physical activity measured through a physical activity monitor (Actigraph GT9X) worn for 7 days from Screening (Visit 1), for 7 days from Randomisation (Visit 2), 7 days from Visit 3, and for 7 days prior to last clinic Visit (Visit 5). • The total duration of subject participation in the study will be approximately 29 to 35 weeks consisting of 6 weeks pre-screening if necessary, 4 weeks run-in, 24 week treatment and one week Follow-Up.
Dosing :	
 • The following study medications will be used in this study: 
 - UMEC/VI 62.5/ 25mcg administered via ELLIPTA - UMEC 62.5 mcg administered via ELLIPTA - Salmeterol 50 mcg administered via DISKUS - Placebo via ELLIPTA - Placebo via DISKUS 
Subjects will be instructed to take one dose of medication each morning from the ELLIPTA (one inhalation equals one dose), and one dose in the morning and one in the evening from the DISKUS.
 
The ELLIPTA will provide a total of 30 doses and the DISKUS will provide a total of 60 doses.

Overview of Key Study Design Features	
Treatment Assignment:	
 • Subjects will be randomly assigned to one of the blinded study treatment regimens in equal proportion (ratio of 1:1:1): 
 - UMEC/VI 62.5/25 mcg once daily via ELLIPTA + placebo twice daily via DISKUS - UMEC 62.5 mcg once daily via ELLIPTA + placebo twice daily via DISKUS - Salmeterol 50 mcg twice daily via DISKUS + placebo once daily via ELLIPTA • GSK RandAll NG used to generate randomisation schedules. • Centralised randomisation within country using GSK RAMOS NG for treatment allocation. • Stratified by long-acting bronchodilator usage during run-in (none or one long-acting bronchodilator per day), country and activity subset (activity subset or no activity subset). Note the activity subset was only included as a randomisation stratification group for logistical purposes.
Interim Analysis	
 • No interim analysis will be performed.

2.4. Statistical Hypotheses

The primary purpose of this study is to demonstrate improvements in lung function for subjects treated with UMEC/VI compared with UMEC for 24 weeks.

The primary endpoint is change from baseline in trough FEV₁ at Week 24.

The null hypothesis is no difference between treatment groups ($H_0: \mu_T - \mu_S = 0$), with the alternative hypothesis that there is a difference between treatment groups ($H_1: \mu_T - \mu_S \neq 0$), where μ_T is the mean change from baseline for UMEC/VI and μ_S is the mean change from baseline for UMEC.

In order to account for multiplicity across treatment comparisons and endpoints, a step-down closed testing procedure will be applied whereby inference for secondary endpoints or treatment comparisons are dependent upon statistical significance having been achieved for the primary comparison. If the primary comparison is significant i.e. the associated p-value for UMEC/VI versus UMEC for change from baseline in trough FEV₁ at Week 24 is below 0.05, this will allow inference of treatment comparisons (UMEC/VI versus UMEC on all secondary endpoints, and UMEC/VI versus Salmeterol and UMEC versus Salmeterol on all primary and secondary endpoints), which will be declared statistically significant if the associated p-value is below 0.05.

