2. SUMMARY OF KEY PROTOCOL INFORMATION

2.1. Changes to the Protocol Defined Statistical Analysis Plan

Changes from the originally planned statistical analysis specified in the protocol are outlined in [Table 1](#).

Table 1 Changes to Protocol Defined Analysis Plan

Protocol	Reporting & Analysis Plan	
Statistical Analysis Plan	Statistical Analysis Plan	Rationale for Changes
	
 An additional population has been defined, the Activity Monitoring (AM) Population, which will comprise all subjects in the ITT population who provide data from at least one activity monitoring session. 	
 Population needed for subset of subjects participating in Activity Monitoring.
	
 All other Endpoints promoted to secondary endpoints 	
 Study aims have developed since protocol and thus previous endpoints classed as 'other' have further importance
	
 An analysis by Maintenance Naive (MN) and Non-Maintenance Naive subgroups have been included. 	
 To investigate prospectively the 1st line use of LAMA/LABA in all symptomatic subjects (no existing data the literature to our knowledge)
	
 An analysis of ratio of trough FEV1 to baseline trough FEV1 	
 To investigate trough FEV1 ratio change from baseline

 Intent-to-treat ICS free (ITT ICS free) 	
 Population excluded. 	
 G-BA analysis to be conducted on the ITT population due to a change in G-BA guidance.

 To compare albuterol/salbutamol use captured in the eDiary with the electronic metered dose inhaler (eMDI) Device as data allow 	
 Not included in this RAP. 	
 Will be included in a supplementary RAP if deemed necessary.

Protocol	Reporting & Analysis Plan	
Statistical Analysis Plan	Statistical Analysis Plan	Rationale for Changes

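### SAP 2.4 claims a step-down closed procedure across endpoints, but after one gate every secondary test is judged at an unadjusted 0.05, so familywise error across the secondary endpoints is not controlled

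*SAP*

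**What the plan says.** Section 2.4 (Statistical Hypotheses) sets the multiplicity rule in two sentences.

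- The first names the method and its scope: "In order to account for multiplicity across treatment comparisons and endpoints, a step-down closed testing procedure will be applied". It then explains that "inference for secondary endpoints or treatment comparisons are dependent upon statistical significance having been achieved for the primary comparison".
- The second gives the decision rule. If the p-value for UMEC/VI versus UMEC on change from baseline in trough FEV1 at Week 24 "is below 0.05, this will allow inference of treatment comparisons". The set that opens is "UMEC/VI versus UMEC on all secondary endpoints, and UMEC/VI versus Salmeterol and UMEC versus Salmeterol on all primary and secondary endpoints", each of "which will be declared statistically significant if the associated p-value is below 0.05".

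The alternative is two-sided: "with the alternative hypothesis that there is a difference between treatment groups". Section 5.5 (Multiple Comparisons and Multiplicity) adds nothing and refers back to 2.4. Section 7.2.1 lists the secondary endpoints, the last being "19) Subject global rating of change in COPD severity". Table 1 in Section 2.1 records "All other Endpoints promoted to secondary endpoints".

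**The concern.** A closed test needs a level-0.05 test of every intersection of the hypotheses in the family. A step-down test needs an order or thresholds that change from step to step. Beyond the gate, Section 2.4 has neither for the secondary endpoints. If two secondary nulls are both true, the rule makes an error when either p-value falls below 0.05, so their joint error exceeds 0.05 unless the two tests are perfectly dependent.

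The gate limits error on the secondary endpoints only when the primary null is true. The trial is run in the expectation that it is false. In that case nothing stands between the secondary tests and an unadjusted 0.05.

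At stake is how patient-reported outcomes, exacerbations, clinically important deterioration (CID), rescue use, FVC and IC will be read. A report that follows this text would call such results statistically significant under a procedure said to account for multiplicity across endpoints, and it does not have that property.

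**Working it through.** **Inputs from the SAP**
- Threshold: 0.05 two-sided for the primary test and for each later test (2.4).
- Comparisons: three (2.4). Allocation 1:1:1 (2.3). No interim analysis (2.3).
- Secondary endpoints: 19 numbered items (7.2.1). This is a minimum, because E-RS subscales and the CID versions and components sit inside single items, and visits are not counted.

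**Assumption.** The SAP gives no correlation between endpoints, so a range from 0 to 0.9 is used.

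**1. The plan's own figure.** The primary test is one test at 0.05 with no alpha spent elsewhere, so its error is 0.05. If every null is true, any false claim must first pass the gate. Simulated familywise error is then 0.050 to 0.051.

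**2. The three comparisons on Week 24 trough FEV1.**
- UMEC/VI = UMEC = salmeterol: an error requires passing the gate, so error is at most 0.05.
- UMEC/VI = UMEC, salmeterol different: the only true null is the primary one, tested at 0.05.
- UMEC/VI differs from UMEC: salmeterol cannot equal both, so at most one salmeterol null is true, tested at 0.05.

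Error is at most 0.05 in each case, so the gate controls this family.

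**3. Number of tests opened by the gate.** Secondary: 19 × 3 = 57. With the two salmeterol tests on the primary endpoint: 57 + 2 = 59.

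**4. One null secondary endpoint, gate passed.** With equal arms, at least one of the three pairwise tests is significant when the range of three independent standard normals exceeds 1.96 × √2 = 2.77. That probability is 0.122.

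**5. Many null secondary endpoints, gate passed.** The primary effect is taken as real. The FEV1 ratio (item 16) is excluded because it cannot then be null in all arms. That leaves 18 endpoints and 18 × 3 = 54 tests. Expected false positives: 54 × 0.05 = 2.7, whatever the correlation. At correlation 0:
- All three comparisons: 1 − (1 − 0.122)^18 = 0.90.
- UMEC/VI versus UMEC alone: 1 − 0.95^18 = 0.60.

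At other correlations, three equal arms were simulated with shared arms built in:

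| Assumed correlation | All three comparisons | UMEC/VI versus UMEC alone |
|---|---|---|
| 0 | 0.90 | 0.60 |
| 0.5 | 0.71 | 0.40 |
| 0.8 | 0.44 | 0.22 |
| 0.9 | 0.33 | 0.15 |

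**6. Sensitivity to the endpoint set.** Item 12, the CID composite, includes FEV1 and may also not be null. Dropping it leaves 17 endpoints, 51 × 0.05 = 2.55 expected false positives, and 1 − (1 − 0.122)^17 = 0.89 at correlation 0. The conclusion does not depend on that item.

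**The case against.** The strongest defence is that the rule is stated openly, the primary test is sound, and the gate does real work. Most of this stands.

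- **Primary endpoint.** A reader might infer that every claim against salmeterol is nominal. That is not so for Week 24 trough FEV1, where step 2 shows that all three comparisons are controlled.
- **Size.** A reader might count subscales and components (E-RS total and three subscales, for scores and for responders; three CID composites with four components), reach 30 endpoints and 30 × 3 + 2 = 92 tests, and quote 1 − 0.95^92 = 0.99. That case cannot arise here. Pairwise tests in three arms share data and are not independent. The FEV1 tests cannot all be null once the primary effect is real. If every null including the primary one is true, the gate holds error at 5%.
- **Promotion of endpoints.** A reader might infer from Table 1 that promoting the former other endpoints enlarged the uncontrolled family. Section 5.5 already places other endpoints under the inference rules of 2.4, and Table 1 does not say how many moved, so this SAP does not settle it.
- **Status of the claims.** The SAP does not call secondary results confirmatory, and exploratory endpoints lie outside the rule.

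None of this supplies control across the secondary endpoints. Gatekeeping protects a second family only if that family is itself tested at level 0.05, and Section 2.4 gives no such test. Being open about the 0.05 threshold does not make the stated property true.

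**Conclusion.** Wrong as written. Section 2.4 attributes to its procedure a control across endpoints that the procedure lacks. With a real primary effect and 18 null secondary endpoints, the chance of at least one false claim is about 0.33 to 0.90 over the three comparisons and about 0.15 to 0.60 for UMEC/VI versus UMEC alone. A single null endpoint already gives 0.12.

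The sizes rest on an assumed common correlation between 0 and 0.9, equal arms, and all 18 endpoints being null. Fewer null endpoints would lower them. The absence of an order, a split or adjusted thresholds is read from the text and needs no assumption.

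It should be fixed, but it does not threaten the trial's main result: the primary conclusion and the two salmeterol comparisons on Week 24 trough FEV1 are unaffected.

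**What to change.** Before unblinding, revise both multiplicity sentences of Section 2.4, since the claim stands in the first and the decision rule in the second:

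1. State that 5% familywise control covers only the three pairwise comparisons on Week 24 trough FEV1, with the two salmeterol tests made only after the gate is passed.
2. Remove the claim that a step-down closed procedure accounts for multiplicity across endpoints.
3. Report all secondary-endpoint p-values as nominal, and do not declare them statistically significant.

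If the sponsor wants controlled secondary claims, it can instead add a short fixed sequence after the gate. Each step names the endpoint, comparison and time point and is tested at 0.05, testing stops at the first p ≥ 0.05, and everything else is nominal. Which endpoints to name, and in what order, is the sponsor's choice.

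Align Section 5.5, which still mentions other endpoints although Table 1 has made them secondary.

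The cost is wording only, with no change to data collection or models. The downside is that fewer secondary results can be called statistically significant.
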